12.2.1.4 Follow-up evaluation

Potential drug-induced liver injury events require follow-up monitoring as described in [Table 12–3](#). Monitoring should continue until liver chemistry values normalize, stabilize, or return to Baseline. Determination of stabilization is at the discretion of the Investigator in consultation with the hepatologist (as applicable) and UCB responsible physician, as needed.

12.3 Other safety measurements

12.3.1 Assessment and management of TB and TB risk factors

All subjects will be assessed for TB at Screening and at the time points specified in the Schedule of Assessments (Table 5–1) through physical examination for signs and symptoms of TB, chest x-ray (Section 12.3.1.2), laboratory testing (Section 12.3.1.1), and subject questionnaire (Section 12.3.1.3).

At Screening, all subjects will have an IGRA test (QuantiFERON TB test is recommended), a chest x-ray (unless already performed within 3 months of Screening) and examination for signs and symptoms of TB. In addition, each subject will complete a TB questionnaire directed at potential exposure and symptoms of TB.

For the purposes of this study, TB definitions are as follows:

- a. Known TB infection:
 - Active TB infection or clinical signs and symptoms suspicious for TB (pulmonary or extra-pulmonary).
 - History of active TB infection involving any organ system or findings in other organ systems consistent with TB infection, unless adequately treated and proven to be fully recovered upon consult with a TB specialist.
 - Any evidence by radiography or other imaging modalities consistent with previously active TB infection that is not reported in the subject's medical history.
 - b. High risk of acquiring TB infection:
 - Known close exposure to another person with active TB infection within the 3 months prior to Screening.
 - Time spent in a healthcare delivery setting or institution where individuals infected with TB are housed and where the risk of transmission of infection is high.
 - c. Latent TB infection (unless appropriate prophylaxis is initiated at least 8 weeks prior to IMP dosing and continued to completion of prophylaxis):
 - The absence of signs, symptoms, or physical findings suggestive of TB infection with a positive IGRA test (or 2 indeterminate IGRA test results) and a chest x-ray (or other imaging) without evidence of TB infection. If the result of the IGRA test is indeterminate, the particular IGRA test previously performed may be repeated once; if positive or indeterminate on retest, the subject may not be randomized to IMP without further evaluation by a TB specialist and discussion with the Study Physician, if LTB infection is identified. The retest must be done during the protocol-defined Screening window.
- Note: If available, respiratory or other specimens must also be smear and culture negative for TB (CDC diagnosis of LTB infection) <http://www.cdc.gov/TB/topic/testing/default.htm>.
- d. NTMB infection is defined as a clinical infection caused by mycobacterial species other than those belonging to the Mycobacterium tuberculosis complex.
 - e. Tuberculosis test conversion:

-
- A positive IGRA result for the current test when previous IGRA test results were negative. All subjects with TB test conversion must immediately stop IMP administration and be referred to a TB specialist for further evaluation. Confirmed TB test conversions should be classified as due to LTBI, active TB infection, or NTMB, and reported to the UCB PS function.

Subject eligibility, retesting requirements, and treatment requirements are depicted in [Figure 12-1](#).

This document cannot be used to support any marketing authorization application and any extensions or variations thereof.

REDACTED COPY

Figure 12-1: Schematic diagram of TB test results and study eligibility

IGRA=interferon-gamma release assay; TB=tuberculosis

^a IGRA retest must be done during the protocol-defined Screening window

^b Subjects with LTBI may enter the study only after they have completed at least 8 weeks of appropriate prophylactic therapy and thereafter, will continue and complete the entire regimen.

12.3.1.1 Tuberculosis assessment by IGRA

During conduct of the study, the TB assessment by IGRA (QuantiFERON TB test is recommended) will be performed as described in [Table 5–1](#) for all subjects. The test results will be reported as positive, negative, or indeterminate. Positive and indeterminate TB test results must be reported as an AE and appropriately updated once the final diagnosis is known (e.g. active TB, latent TB, or false positive TB test). UCB also recommends that a TB specialist be consulted where TB (latent or active) is suspected or if there are doubts regarding test results. If latent or active TB is identified, subject must undergo appropriate study-specified withdrawal procedures. The retest during Screening must be done during the protocol-defined Screening window.

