5.2.2 Double-blind Initial Treatment Period

During the active-controlled 16-week Initial Treatment Period, approximately 450 subjects will be randomized 1:1:1 to receive the following blinded IMP regimens:

- Bimekizumab 320mg administered Q4W throughout the study (150 subjects)
- Bimekizumab 320mg administered Q4W until Week 16 (150 subjects)
- Adalimumab 80mg administered as an initial dose, followed by 40mg Q2W starting 1 week after the initial dose (ie, adalimumab will be administered according to the labeling recommendations) until Week 24 (150 subjects)

Investigational medicinal products will be administered in the clinic by sc injection at the time points specified in the schedule of study assessments (Table 5-1).

Subjects will be followed in a double-blind fashion. Subjects may receive placebo injections at certain visits in order to blind the IMP. The assessments to be performed at each Initial Treatment Period Visit are presented in Table 5-1.

The active comparator-controlled Initial Treatment Period will be used to demonstrate the efficacy of bimekizumab versus adalimumab. Efficacy of bimekizumab versus adalimumab will be measured at Week 16 because it was the time point for the primary endpoint in prior pivotal studies of adalimumab in PSO where efficacy was demonstrated.

Subjects withdrawing early from the study will undergo the PEOT Visit assessments and will enter the SFU Period. Subjects withdrawing early from the study will not be eligible for inclusion in the open-label study.

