9. There is confirmation of a pregnancy during the study, as evidenced by a positive pregnancy test (see [Section 12.1.4](#) for more information regarding pregnancies).
10. A subject considered as having either a suspected new LTB infection or who develops active TB or NTMB infection during the study (including but not limited to, conversion demonstrated by IGRA or other diagnostic means) must be immediately discontinued from IMP and a PEOT Visit must be scheduled as soon as possible, but not later than the next regular visit.

The subject must be permanently withdrawn if further examinations result in a diagnosis of active TB, or if the subject is diagnosed with latent TB infection (LTBI) with no initiation of prophylactic treatment, prematurely discontinues prophylactic treatment, or, in the opinion of the Investigator or Sponsor, is noncompliant with prophylactic TB therapy.

Confirmed active TB is an SAE and must be captured on an SAE Report Form and provided to the Sponsor in accordance with SAE reporting requirements. As with all SAEs, periodic follow-up reports should be completed as per protocol requirements until such time as the TB infection resolves.

Additional information on TB policies is provided in [Section 12.3.1](#).

11. Subjects with newly diagnosed inflammatory bowel disease (IBD) or with IBD flares during the study must:
 - Be referred, as appropriate, to a health care professional treating IBD, such as a gastroenterologist
 - Discontinue IMP and be followed-up until resolution of active IBD symptoms

If IBD flares increase in severity or frequency during the study, the Investigator should use clinical judgement in deciding whether the subject should continue in the study and contact the

Medical Monitor and UCB study physician to confirm the subject's suitability for continued participation in the study.

12. Subjects **must be referred** immediately to a mental health care professional and may be withdrawn from the study based upon the Investigator's judgment of benefit/risk for:

- Active suicidal ideation as indicated by a positive response ("Yes") to Question 4 of the "Since Last Visit" version of the eC-SSRS.
- Moderately severe major depression as indicated by a PHQ-9 score of 15 to 19 if this represents an increase of 3 points compared to last visit.

13. Subjects must be referred immediately to a mental healthcare professional and must be withdrawn in case of:

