8.4 Premature End of Treatment Visit

If a subject is withdrawn from the study:

- The subject will be withdrawn from IMP, will undergo the same assessments as the Week 56 visit (see [Section 8.3.12](#)), and will enter the SFU Period.
- The subject will be encouraged to return for the SFU Visit (20 weeks after the last received dose; see [Section 8.5](#)).

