12.3.1.4 Tuberculosis management

During the study, subjects who develop evidence of LTB infection or active TB must immediately stop further administration of IMP and will be referred to an appropriate TB specialist (pulmonologist or infectious disease specialist) for further evaluation. Evidence of LTB infection is defined as subject's IGRA test converts to positive or indeterminate (and confirmed indeterminate on repeat), or the subject's questionnaire or history and physical indicates that TB infection or exposure may have occurred. Evidence of active TB includes, in addition to the aforementioned tests, signs and symptoms of organ involvement. In either situation, the subject should be carefully assessed by a TB specialist for active TB. Subjects diagnosed with active TB should be withdrawn from the study and receive appropriate TB or prophylaxis therapy.

If a TB specialist excludes an active TB infection the subject can proceed with the IMP no earlier than 4 weeks after the start of an appropriate prophylactic therapy.

Any presumptive diagnosis or diagnosis of a TB infection is a reportable event. Confirmed active TB must be reported as an SAE. The Investigator is to complete and submit the TB Follow-Up Form provided.

The subject should be transferred to the care of his/her physician and managed according to the best available standard of care. Subjects identified as having converted to active TB during the study must be withdrawn and scheduled to return for the PEOT Visit as soon as possible but no later than the next scheduled study visit and complete all PEOT Visit assessments.

The subject should be encouraged to complete a SFU Visit (20 weeks after the final dose of IMP).

If infection with NTMB is identified during the study, the same procedure as for active TB acquired during the study must be followed.

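### The protocol is internally inconsistent on latent TB found on study: one section points to withdrawal, another lets IMP resume, and suspicion alone triggers a study-withdrawal visit

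*Protocol*

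**What the plan says.** The current text deals with latent TB suspected or found on study in these places:

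- **Protocol 12.3.1.1 (IGRA testing).** "If latent or active TB is identified, subject must undergo appropriate study-specified withdrawal procedures". Latent and active infection are named together, and prophylaxis makes no difference.
- **Protocol 12.3.1.4 (TB management).** A subject with evidence of either condition "must immediately stop further administration of IMP" and is referred to a TB specialist. Then: "Subjects diagnosed with active TB should be withdrawn from the study and receive appropriate TB or prophylaxis therapy". Latent infection is not named in that sentence. If the specialist excludes active infection, "the subject can proceed with the IMP no earlier than 4 weeks after the start of an appropriate prophylactic therapy". A PEOT Visit is specified only for conversion to active TB, with nontuberculous mycobacterial infection handled the same way.
- **Protocol 6.3 item 10.** A subject with a suspected new latent infection, active TB or nontuberculous infection "must be immediately discontinued from IMP and a PEOT Visit must be scheduled as soon as possible". Permanent withdrawal follows for active TB, "or if the subject is diagnosed with latent TB infection (LTBI) with no initiation of prophylactic treatment", or if prophylaxis is stopped early or not complied with.
- **Protocol 8.4 (and 5.2.5).** The PEOT Visit procedure opens with "If a subject is withdrawn from the study". The subject comes off IMP, has the Week 56 assessments and enters the SFU Period.
- **Protocol 5.2.2.** "Subjects withdrawing early from the study will not be eligible for inclusion in the open-label study".

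**The concern.** A site that learns of a possible latent infection needs to know three things: whether the subject leaves the study, whether IMP may be given again, and which visit to schedule. The sections give different answers to all three. At stake is whether a subject under evaluation for TB is exposed again to an immunomodulator, and whether that depends on which section the site reads. Access to the open-label study turns on the same question. A lesser statistical issue is whether a temporary stop counts as treatment discontinuation, since discontinuation leads to NRI.

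**Working it through.** The plan states no figure on this point, so the check is a side-by-side reading of the current text, following one subject through it. Assume a suspected new latent infection, later confirmed as latent, with active TB excluded and prophylaxis started and complied with.

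**Step 1. Immediate action.** Sections 6.3 item 10, 12.3.1 (item e, test conversion) and 12.3.1.4 all stop IMP at once. They agree.

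**Step 2. Does the subject leave the study?**
- 12.3.1.1: withdrawal procedures apply, on the same terms as for active TB.
- 12.3.1.4: withdrawal from the study is stated for active TB only.
- 6.3 item 10: none of the conditions for permanent withdrawal is met, so by implication the subject is not permanently withdrawn.

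**Step 3. May IMP be given again?**
- 12.3.1.4: expressly yes, after the stated interval on prophylaxis.
- 6.3 item 10: yes by implication only.
- 12.3.1.1: no provision for it.

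**Step 4. Which visit?**
- 6.3 item 10: a PEOT Visit, already on suspicion and no later than the next regular visit.
- 12.3.1.4: a PEOT Visit only for conversion to active TB.
- 5.2.5 and 8.4: the PEOT Visit is for subjects leaving the study and is followed by SFU. No section describes a return to IMP after it.

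Item 10 is therefore at odds with itself once 8.4 is applied. It orders a study-withdrawal visit on suspicion, then makes permanent withdrawal conditional on what is found later. A subject allowed to resume under 12.3.1.4 may already have been processed as withdrawn.

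**Step 5. Open-label study.** If the PEOT Visit counts as early study withdrawal, Section 5.2.2 bars the subject. That sentence stands under the Initial Treatment Period, but Section 5.2 also places open-label entry after completion of the Maintenance Treatment Period.

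**Step 6. When does it matter?**
- *Before Week 52.* Under 12.3.1.4, evidence of latent infection includes the questionnaire, history and physical examination. The questionnaire is given at Weeks 12, 24, 36 and 48 (Sections 8.2.8, 8.3.4, 8.3.7, 8.3.10). Doses remain after each of these visits, so the choice of section changes dosing.
- *Week 52 IGRA.* This is the only scheduled on-study IGRA (Section 8.3.11), and Week 52 is the last dosing visit (Section 7.2). If prophylaxis starts at Week 52, resumption is possible at 52 + 4 = Week 56 at the earliest, when no dose remains in this study. What is left is mainly open-label eligibility.

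**Step 7. Week 56 analysis of a Week 52 converter.** The PEOT Visit has the Week 56 assessments and is due by the next regular visit, which is Week 56. SAP 3.3 maps an early-withdrawal visit to the next scheduled visit and treats it as observed there. For subjects who stop treatment but stay in the study, SAP 4.2.1 sets efficacy data to missing only after the last treatment date + 35 days. Week 52 to Week 56 is 4 × 7 = 28 days, or 28 + 7 = 35 days if Week 52 is on schedule and Week 56 falls at the end of its window. Either handling can therefore give observed Week 56 data.

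**Step 8. Earlier interruptions.** If prophylaxis starts at Week 12, IMP could resume at 12 + 4 = Week 16 at the earliest. Protocol 14.3.1 and SAP 8.1.2 count withdrawal from treatment before Week 16 as nonresponse. Neither says whether a temporary stop for suspected TB is such a withdrawal.

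**The case against.** The best defence is that Section 12.3.1.1 creates no rule of its own. It refers to the study's specified withdrawal procedures, which can be read as a pointer to Section 6.3. Item 10 there sits in a list about withdrawal from IMP and separates an immediate stop from permanent withdrawal. On this reading 6.3 and 12.3.1.4 agree on who is permanently withdrawn: stop, evaluate, withdraw if TB is active or prophylaxis fails, otherwise resumption is possible.

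Much of that stands. A reader might infer that 12.3.1.1 flatly requires study withdrawal for latent TB; its wording is too indirect for that. A reader might also infer that 12.3.1.4 lets IMP continue without interruption; it does not, because the stop comes first. The defence does not dispose of the visit problem, though. Item 10 still requires on suspicion a visit that 5.2.5 and 8.4 reserve for subjects leaving the study, and 12.3.1.4 triggers that visit differently.

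A stronger statistical reading is also tempting: that the conflict decides the Week 56 results and shifts response rates by a calculable amount. The documents do not support it. They give no conversion rate. Any total would also need every converter to be a responder who is then scored a nonresponder, and the SAP mapping and 35-day rules work against that. Protocol 14.3.2.1.2 and 14.7 do apply NRI to subjects who discontinue before Week 56, but a subject treated at Week 52 has had every scheduled dose. Week 56 PASI90 and IGA are descriptive only (SAP 8.2.2.1) and outside the testing sequence H1 to H12.

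**Conclusion.** The point holds as an internal inconsistency in the current protocol text. For one and the same finding, the sections differ on whether the subject leaves the study, whether IMP may be resumed and which visit takes place, and they leave open-label eligibility unclear. The inconsistency over the PEOT Visit does not depend on how 12.3.1.1 is read. The practical effect on dosing lies mainly with cases found before Week 52; for Week 52 IGRA conversions it is mainly open-label eligibility.

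No numerical size is assigned. The number of subjects affected is not in the documents and is probably small, and no effect on power, type I error or a hypothesis test is asserted. The NRI question in Step 8 is a gap worth closing, not evidence of bias. No view is taken on which clinical rule is right. The change should be made because it concerns patient safety and consistency between sites.

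**What to change.** Reconcile Protocol Sections 6.3 item 10, 5.2.5, 8.4, 12.3.1.1 and 12.3.1.4 so that latent TB found on study has one stated path. State whether the visit required on suspicion is a PEOT Visit or an unscheduled visit, and what follows for open-label eligibility. The sponsor's medical team decides the clinical content.

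Optionally, add one sentence to the SAP saying whether a temporary stop of IMP for suspected TB counts as treatment discontinuation for NRI.

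The cost is a wording clarification in the protocol and at most one SAP sentence. No test or visit needs to be added for this purpose.

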12.3.1.2 Chest x-ray for tuberculosis

A plain posteroanterior chest x-ray must be performed in the Screening Period unless one has been performed within 3 months prior to the Screening Visit. The chest x-ray (or, if done, Computed Axial Tomography [CAT] of the Chest) must be clear of signs of TB infection (previous or current) before first IMP administration. All chest imaging (particularly x-rays) should be available for review by the Investigator before randomization of the subject. The chest x-ray reading should be repeated if the TB test was confirmed positive. If the second read of the pretreatment chest x-ray is confirmed to be clear, the subject may be included in the study 8 weeks after the start of the TB prophylactic treatment. If the pretreatment chest x-ray is not available for a re-read, it should be repeated after notification to the radiologist that this subject is IGRA positive, and confirmed to be clear for signs of TB.

The chest imaging must be negative for any old or recent TB infection as determined by a qualified radiologist and/or pulmonary physician. Any new clinically significant findings post Baseline on chest x-ray must be documented in the source documents and the eCRF as an AE.

12.3.1.3 Tuberculosis questionnaire

The questionnaire “Evaluation of signs and symptoms of tuberculosis” should be used as a source document. The questionnaire will be completed as described in [Table 5–1](#). The questionnaire will assist with the identification of subjects who may require therapy for TB. A subject who answers “Yes” to the question “Has the subject been in close contact with an individual with active TB, or an individual who has recently been treated for TB?” at Screening is excluded. A “Yes” response to any of the other questions within the questionnaire at Screening should trigger further careful assessment to determine if subject has LTB or active TB (see Exclusion Criterion #12 [Section 6.2](#)). A “Yes” response to any of the questions during the study should trigger further assessments to determine if the subject has either LTB or active TB infection.

12.3.1.4 Tuberculosis management

During the study, subjects who develop evidence of LTB infection or active TB must immediately stop further administration of IMP and will be referred to an appropriate TB specialist (pulmonologist or infectious disease specialist) for further evaluation. Evidence of LTB infection is defined as subject's IGRA test converts to positive or indeterminate (and confirmed indeterminate on repeat), or the subject's questionnaire or history and physical indicates that TB infection or exposure may have occurred. Evidence of active TB includes, in addition to the aforementioned tests, signs and symptoms of organ involvement. In either situation, the subject should be carefully assessed by a TB specialist for active TB. Subjects diagnosed with active TB should be withdrawn from the study and receive appropriate TB or prophylaxis therapy.

If a TB specialist excludes an active TB infection the subject can proceed with the IMP no earlier than 4 weeks after the start of an appropriate prophylactic therapy.

Any presumptive diagnosis or diagnosis of a TB infection is a reportable event. Confirmed active TB must be reported as an SAE. The Investigator is to complete and submit the TB Follow-Up Form provided.

The subject should be transferred to the care of his/her physician and managed according to the best available standard of care. Subjects identified as having converted to active TB during the study must be withdrawn and scheduled to return for the PEOT Visit as soon as possible but no later than the next scheduled study visit and complete all PEOT Visit assessments.

The subject should be encouraged to complete a SFU Visit (20 weeks after the final dose of IMP).

If infection with NTMB is identified during the study, the same procedure as for active TB acquired during the study must be followed.

